### 9.3.2 Comparison of Treatment Groups

Comparisons will be made between TEOSYAL® RHA Redensity and the control.

### 9.3.3 Descriptive Statistics

Descriptive statistics (i.e., frequency and percent) will be calculated for each treatment group. Quantitative variables will be presented by way of number of observations, number of missing values, mean, standard deviation, extreme values (minimum and maximum), median, and 95% confidence interval. Categorical data will be presented by way of number of observations, number of missing values, and for each observed category, the number of occurrences and its corresponding percentage.

### **9.3.5 Discontinuation and Drop-Outs**

A dropout rate of up to 20% is assumed. Dropouts will not be replaced. All available data from dropouts will be included in the ITT analysis. The disposition of subjects will summarize the number of subjects enrolled and discontinued.

### **9.3.6 Multiple Comparisons**

No methods will be used to accommodate multiplicity (unless otherwise specified).

### **9.3.7 Multicenter Data**

The data will be pooled across centers for analysis. Additionally, data for each center will be provided in data listings.

### **9.3.8 Pooling of Data from US and Canadian Sites**

In order to establish if safety and efficacy data from the US and Canada can be combined, homogeneity of various baseline characteristics across the two countries will be explored (i.e., age, BMI, smoking history, alcohol history, sun exposure, and surgical/procedure history\*).

\* Surgical/procedure history limited to any previous facial and/or cosmetic surgery/procedures (e.g., facial aesthetic procedures such as laser/toxin/filler, rhytidectomy, blepharospasm, dental surgery, breast enhancement, etc.).

Ethnicity, race and Fitzpatrick Skin Type do not need to be proportionately balanced between US sites and Canadian sites; however, the predefined minimal sample of subjects with Fitzpatrick Skin Types IV, V and VI must still be obtained in the subject population overall.

Testing will be performed with the null hypotheses being the absence of differences between the US and Canada. All observed two-sided p-values must be  $>0.05$  to pool data; if the two-sided p-value is  $\leq 0.05$ , data collected from subjects of both countries will not be pooled unless further argumentation could be provided to support such pooling. Percentages of each characteristic will be compared using a Fischer's exact test, and continuous data will be compared using a Student t-test (or Mann-Whitney test if not normally distributed).

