11.6 General Considerations

Data will be listed by treatment group and subject number. The safety and efficacy data will be summarized by treatment allocation. Descriptive statistics will consist of values, tables, mean, standard deviation, minimum and maximum for continuous variables, and frequency and percent for discrete variables.

A full description of the statistical methods planned for this study will be provided in the Statistical Analysis Plan (SAP). All programs for data output and analyses will be written in SAS version 9.3 or higher (SAS Institute, Inc., Cary, NC).

Missing Values

For subjects lost-to-follow-up (LTFU), or not present at a visit, missing data will be imputed using last observation carried forward (LOCF) for the primary endpoint (PR-SRS, ITT population). Various statistical procedures to confirm the impact of missing data (e.g., Tipping Point Analysis) will be detailed in the Statistical Analysis Plan. No imputations will be performed for secondary endpoints; analyses will utilize available data as observed.

Discontinuation and Drop-Outs

Dropouts will not be replaced. All available data from dropouts will be included in the ITT analysis. Subject disposition will be summarizing the number of subjects enrolled in the study and those that discontinued the study and their reason.

Interim Analysis

[figure not shown]
[figure not shown]
[figure not shown]
There will be no interim efficacy analysis.

Poolability Between Countries

Due to the potential impact on safety and effectiveness, the variation in data across baseline demographics will be accounted, and heterogeneity across the two countries (US and Canada) will be investigated to establish if the data for safety and effectiveness can be combined.

To assess the homogeneity of the baseline characteristics across the two countries, and to determine if data from both countries could be pooled, statistical hypothesis tests will be performed with their null hypotheses as the absence of difference between US and Canada. All observed two-sided p-value must be >0.05 to pool data from the two countries. If the two-sided p-value is less or equal to 0.05, then, data collected from subjects of both countries will not be pooled. Percentages of each characteristic of the demographics will be compared using a Fischer's Exact test, and continuous data will be compared using a Student t test. The full details will be provided in the Statistical Analysis Plan.

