11.8 Safety Analysis

[REDACTED]

[REDACTED]

The study will be able to detect any AE that has an incident rate of <1.0% (0.625%) or more (assuming 200 subjects will be treated with the investigational device in the two pooled arms and taking [REDACTED]

[REDACTED]

[REDACTED]

[REDACTED]

[REDACTED]

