13 STUDY MANAGEMENT & ADMINISTRATIVE REQUIREMENTS

13.1 Protocol Amendments

No amendments to the protocol will be implemented without the prior written consent of the Sponsor. Should an amendment be necessary, the reviewing IRB, Health Canada and FDA may require review and approval prior to its implementation.

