## 1. INTRODUCTION

This statistical analysis plan (SAP) gives a comprehensive and detailed description of statistical techniques to be used [REDACTED]. The purpose of this SAP is to ensure the credibility of the study findings by pre-specifying the statistical approaches for the analysis of study data prior to database lock. This SAP provides additional details concerning the statistical analyses outlined in the protocol. Whenever differences exist in descriptions or explanations provided in the protocol and SAP, the SAP prevails.

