## **7. ANALYSIS POPULATIONS**

## 7.1 Populations

Three analysis populations will be defined: Intent-to-Treat (ITT), Per Protocol (PP), and Safety (SAFT). All populations will be defined and determined prior to unblinding for the final analysis.

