## 8. SAMPLE SIZE JUSTIFICATION

The study will ensure that enrolled subjects are representative of U.S. population ethnicity and will be comprised of at least 25% subjects of Fitzpatrick skin IV to VI. In order to be able to detect a sufficient AE rate (i.e., maximum 2.5% in the sub-population of subjects of Fitzpatrick skin type IV to VI), the number of subjects must be increased beyond that required for achieving statistical power for the primary efficacy outcome; specifically:

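### US-Canada pooling depends on six unadjusted baseline tests that fail by chance in about 15% to 24% of trials (assumed settings) and do not test outcomes; failure leads to an undefined exception

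*SAP*

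**What the plan says.** SAP 9.3.8 compares the countries on age, BMI, smoking, alcohol, sun exposure and past facial or cosmetic procedures. Percentages are compared with Fisher's exact test, and continuous variables with a t-test, or Mann-Whitney if not normal. Every two-sided p-value has to exceed 0.05. If one does not, "data collected from subjects of both countries will not be pooled unless further argumentation could be provided to support such pooling". SAP 9.3.6 applies no multiplicity adjustment unless otherwise specified, and 9.3.8 specifies none.

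Protocol 11.6 has the same threshold: "All observed two-sided p-value must be >0.05 to pool data from the two countries". It does not list the variables and has no exception. Where the documents differ, SAP section 1 settles it: "Whenever differences exist in descriptions or explanations provided in the protocol and SAP, the SAP prevails".

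Two nearby provisions matter. SAP 7.1 puts a deadline on the analysis sets: "All populations will be defined and determined prior to unblinding for the final analysis". SAP 9.3.7 states without condition: "The data will be pooled across centers for analysis". The visible text does not say how 9.3.7 fits with 9.3.8.

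**The concern.** - **Chance failure.** Six tests, each at 5%, must all be non-significant. Some trials will fail even when the two countries recruit from the same population.
- **Wrong target.** Pooling is in doubt when response, adverse event rates or the treatment effect differ by country. The six tests look at none of these. The list also leaves out baseline PR-SRS, from which response is defined. It exempts Fitzpatrick type from balance between countries, although the safety sample size is built around types IV to VI.
- **Open consequence.** After a failure, pooling rests on an argument whose content, judge and date are not given in the visible text. Nor does that text say how the three-part success rule in SAP 9.1.1 would apply to unpooled data.

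A chance result on BMI or smoking would therefore put the planned main analysis in doubt, and the choice between pooled and unpooled results could be made after unblinding. The adverse event detection figures also appear to presume pooling.

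**Working it through.** The plan states no failure rate for this rule, so there is none to reproduce.

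**Inputs from the documents.** Six characteristics, a 0.05 two-sided threshold, no adjustment, Fisher or t-test/Mann-Whitney (SAP 9.3.6 and 9.3.8); at least 200 subjects (Protocol 4.2.1).

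**Assumptions.** Country split, prevalences and correlation between characteristics. Age and BMI are treated as continuous and the other four as binary.

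**1. Nominal rate.** Six independent tests at exactly 5%: 1 − 0.95^6 = 26.5%.

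**2. Allowing for Fisher's conservatism.** By enumeration at N = 200, the true size *s* of the Fisher test is 1.7% to 4.5% for splits from 100/100 to 190/10 and prevalences from 5% to 50%. With two exact 5% tests and four independent Fisher tests, the failure rate is 1 − 0.95² × (1 − *s*)^4:

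- 190/10, prevalence 5%: *s* = 0.0174, failure 15.9%
- 100/100, prevalence 10%: *s* = 0.0287, failure 19.7%
- 140/60, prevalence 50%: *s* = 0.0447, failure 24.8%

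**3. Simulation with identical countries.** 20,000 trials per setting, two t-tests and four Fisher tests. Entries are the percentage of trials failing at least one test; *r* is the latent correlation; mixed means 15/30/45/60%.

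| Split | Prevalences | r=0 | r=0.3 | r=0.5 | r=0.7 |
|---|---|---|---|---|---|
| 100/100 | mixed | 22.1 | 21.2 | 18.6 | 17.3 |
| 100/100 | all 10% | 19.5 | 18.7 | 17.9 | 16.0 |
| 100/100 | all 50% | 23.8 | 21.6 | 19.8 | 17.6 |
| 150/50 | mixed | 24.0 | 23.0 | 20.9 | 19.0 |
| 150/50 | all 10% | 23.1 | 22.0 | 21.2 | 18.9 |
| 150/50 | all 50% | 23.6 | 22.8 | 20.5 | 18.0 |
| 180/20 | mixed | 22.3 | 20.9 | 19.1 | 17.0 |
| 180/20 | all 10% | 19.3 | 18.2 | 16.4 | 14.8 |
| 180/20 | all 50% | 21.1 | 19.8 | 17.9 | 16.1 |

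The range is 14.8% to 24.0%. Using Mann-Whitney for both continuous variables (mixed prevalences) gives 17.1% to 23.9%. A separate simulation (8,000 trials per setting; splits 100/100, 140/60, 160/40 and 180/20; correlation 0 to 0.5) gives 15.7% to 25.0%.

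**4. A real but possibly irrelevant difference.** Suppose the countries differ by 0.3 SD in BMI only (assumed, mixed prevalences). The rule then fails in 63% to 64% of trials at 100/100, 54% to 56% at 150/50 and 34% to 37% at 180/20, whether or not BMI affects response.

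**5. Outcome differences missed.** If the treatment effect differs by country for reasons unrelated to the six variables, the rule behaves as in step 3. It passes in 1 − 0.240 = 76% to 1 − 0.148 = 85% of trials.

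**6. Adverse event figures.** The Protocol synopsis takes 200 × 0.8 = 160 treated subjects, and 1/160 = 0.625%, the rate in Protocol 11.8: "The study will be able to detect any AE that has an incident rate of <1.0% (0.625%) or more". A 25% share gives 0.25 × 160 = 40, and 1/40 = 2.5%, the rate in SAP 8: "maximum 2.5% in the sub-population of subjects of Fitzpatrick skin type IV to VI". Both counts take the two countries together.

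**7. Power of an interaction check.** Assume 80% vs 20% response in one country and 60% vs 20% in the other, a 20-point difference in effect.

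- 75/25 subjects per arm in each country: SE = √(0.16/75 + 0.16/25 + 0.24/75 + 0.16/25) = 0.135; power = Φ(0.20/0.135 − 1.96) = 0.32.
- 112/38 and 38/12: SE = √(0.16/112 + 0.16/38 + 0.24/38 + 0.16/12) = 0.159; power = 0.24.

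**The case against.** The strongest reply is that the consequence is small. The SAP exception lets pooling go ahead after a chance failure, no separate analyses are forced, and neither country has to meet the success criteria alone. On this view one sentence naming criteria, decision-maker and date would be enough, and default pooling goes too far because it removes an assessment that Protocol 11.6 promises. That is a fair limit on severity. But it leaves in place a rule that often fails by chance and does not look at outcomes.

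Other points stand in part:

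- The 15% to 24% range depends on the chosen settings and is not an upper limit. The second simulation reaches 25.0%, and coding with more than two levels would move the rate toward or above 26.5%.
- The 76% to 85% pass rate is only the complement of the chance-failure rate. The BMI result shows the rule reacting to a real difference, though one that need not matter for response.
- SAP 9.3.7 concerns centers, and 9.3.8 can be read as the more specific rule, so that tension is modest.
- The divisions 1/160 and 1/40 are inferred; the plan's own calculation is redacted.
- Protocol 11.7, parts of 11.8 and SAP Appendix A are redacted and may hold by-country outcome analyses. Those would not change how often the visible rule fails, and the exception sentence is visible in full.

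**Conclusion.** The concern holds and should be fixed. With identical countries the rule fails in 26.5% of trials under independence and exact test levels, and in about 15% to 24% under the assumed splits, prevalences, correlations and binary coding. It gives no evidence either way on whether response, adverse event rates or the treatment effect differ by country. Failure opens a discretionary decision about the main analysis with no visible criteria or deadline. This does not by itself produce a false efficacy claim. The conclusion concerns the visible rule only.

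**What to change.** Before unblinding, replace the p-value rule in SAP 9.3.8 with wording such as:

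> Data from US and Canadian subjects are pooled across countries within each defined analysis population (ITT, PP, SAFT) for all efficacy and safety analyses.

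Then:

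- Tabulate the six baseline characteristics by country, with no pooling decision attached.
- Report Week 8 BLE responder rates by arm, and key adverse event rates, by country.
- Add a country-stratified (Mantel-Haenszel) risk difference and a treatment-by-country interaction on the Week 8 BLE responder endpoint, both as descriptive consistency checks.
- Align any redacted analysis text.

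If a poolability decision must stay, write its criteria, its decision-maker and a date before unblinding into 9.3.8.

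**Cost.** SAP wording and two or three tables; no new data. Because the SAP takes precedence, the SAP change can suffice for the analysis. Protocol 11.6 would still carry the old rule until it is aligned at the next amendment, for which "the reviewing IRB, Health Canada and FDA may require review and approval prior to its implementation". The formal baseline check is lost, and the interaction check has only 24% to 32% power for a 20-point difference under the assumed rates, so it can only be descriptive.

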### 9.3.9 Visit Windows

### 9.3.10 Dates

Partial dates will be imputed to the lowest available element of time (e.g., month or year). Missing dates will not be imputed. In case of adverse events duration, if the month is missing, the 15 of the month will be used in the calculation of the duration while the 01 of July will be used in case of a missing year.

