9.6.7 Adverse Event Reporting

9.6.7.1 All Adverse Events

All AEs, whether serious or not, will be recorded from the time of informed consent until the last study visit, or until 1 month following the last study treatment. The TI will assess all AEs and record details of seriousness, severity, duration, and action taken with study device, and relationship to the study device. The Sponsor is responsible for reporting AEs to the relevant governing authorities in the time frame applicable according to international and local law.

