### 9.3.12 Outliers

No method to process outliers will be used. Data will be analyzed as reported in the database.

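### The AE-duration date rule in SAP 9.3.10 names each missing element one unit too high, so it cannot be computed, and the evident intention still allows a stop before onset

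*SAP*

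**What the plan says.** SAP 9.3.10 (Dates) has three parts.

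- A general rule: "Partial dates will be imputed to the lowest available element of time (e.g., month or year").
- A limit: "Missing dates will not be imputed".
- A rule for adverse event durations only, with two triggers. The first reads "if the month is missing, the 15 of the month will be used in the calculation of the duration". The second trigger concerns the year and reads "the 01 of July will be used in case of a missing year".

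The AE rule does not mention a missing day. It does not say whether it applies to onset dates, stop dates or both. It sets no bound against consent, onset, stop or last contact.

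Three other places bear on it. Protocol 9.6.7.1 has the Treating Investigator "record details of seriousness, severity, duration, and action taken with study device" for all AEs. SAP 9.3.12 says "No method to process outliers will be used. Data will be analyzed as reported in the database". SAP section 1 says "Whenever differences exist in descriptions or explanations provided in the protocol and SAP, the SAP prevails", so nothing in the protocol would override the date rule.

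**The concern.** This is a derivation rule that a programmer has to code, and it has two separate defects.

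The first is in the literal wording. The element declared missing is the one needed to place the substitute date. Subjects are in the study for 52 to 66 weeks, so participation can span two or more calendar years and a missing year often cannot be inferred from the visit schedule.

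The second appears once the wording is repaired. A mid-month or mid-year substitute can fall on the wrong side of the known date at the other end of the event, which gives a negative duration. No legible text sets such values aside or corrects them. SAP 9.2.1 summarises safety data by mean, standard deviation, minimum and maximum, so if duration is tabulated that way, a negative value could be printed as the minimum. The alternative is to repair such values after the data have been seen, which the SAP's stated purpose of pre-specification is meant to prevent.

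**Working it through.** The plan gives no figure to reproduce, so the check is date arithmetic.

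**Step 1. The rule as written.** Year 2018, month missing, day set to 15: no valid date. Year missing, 1 July: no valid date. Neither case can be computed.

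**Step 2. Each trigger moved down one unit.** Day missing, use the 15th of the known month. Day and month missing, use 1 July of the known year. Duration is stop minus onset.

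| Onset | Stop | Imputed date | Duration |
|---|---|---|---|
| 20 March | day missing, March | stop 15 March | 15 - 20 = -5 days |
| 10 September | year only | stop 1 July | -71 days |
| day missing, March | 5 March | onset 15 March | 5 - 15 = -10 days |

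**Step 3. How often, with the stop day missing.** Assume onset is equally likely on each of 365 days (2018 used as the example year) and the true duration is d days. The result is negative when onset is after the 15th and the event stops in the same month. In a month of m days that is m - d - 15 onset days, if positive. A 365-day year has seven months of 31 days, four of 30 and one of 28.

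| d | Negative onset days | Share of 365 |
|---|---|---|
| 0 | 7×16 + 4×15 + 13 = 185 | 50.7% |
| 3 | 7×13 + 4×12 + 10 = 149 | 40.8% |
| 7 | 7×9 + 4×8 + 6 = 101 | 27.7% |
| 14 | 7×2 + 4×1 + 0 = 18 | 4.9% |
| 21 | 0 | 0% |

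**Step 4. The other partial dates.**

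- Onset day missing, stop known: negative on 14 - d days of each month. For d = 3, 12×11 = 132 (36.2%). For d = 7, 12×7 = 84 (23.0%). For d = 14, none.
- Stop day and month missing: negative when onset is after 1 July and the stop is in the same year, which is 183 - d days. For d = 7, 176/365 = 48.2%. For d = 30, 153/365 = 41.9%.

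**Step 5. Effect on the mean, stop day missing, no bound.** The average day of the month over the year is (7×496 + 4×465 + 406)/365 = 5738/365 = 15.72. Replacing it by 15 shifts the mean by -0.72 day for every d: 3 becomes 2.28, 7 becomes 6.28, 14 becomes 13.28. A missing onset day gives +0.72. Overlong values largely offset the negative ones.

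**Step 6. Effect of not letting the stop fall before onset.** The floor removes every negative value but raises the mean. A month with k negative onset days adds k(k+1)/2 days to the yearly total.

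- d = 0: (7×136 + 4×120 + 91)/365 = 1523/365 = 4.17, so the mean is -0.72 + 4.17 = 3.45.
- d = 3: (7×91 + 4×78 + 55)/365 = 1004/365 = 2.75, so the mean is 2.28 + 2.75 = 5.03.
- d = 7: (7×45 + 4×36 + 21)/365 = 480/365 = 1.32, so the mean is 6.28 + 1.32 = 7.59 before rounding of the parts.
- d = 14: (7×3 + 4×1)/365 = 25/365 = 0.07, so the mean is 13.35.

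When the stop month is missing as well, the floor costs much more. For d = 7 the unbounded mean is 7 - 1 = 6 days, because 1 July lies one day before the average day of the year. The floor adds (176×177/2)/365 = 15576/365 = 42.7 days, giving about 48.7.

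**The case against.** The best defence is that the intent can be recovered. The general sentence works from the elements that are available. If the AE rule is read the same way (month available, use the 15th; year available, use 1 July), the missing-day case is covered and only the wording is at fault. That is a fair account of what was meant, but it is not what the text says, and it leaves the second defect untouched.

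Several stronger readings are tempting and do not hold.

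- *The section contradicts itself.* The ban on imputing missing dates reads naturally as covering wholly missing dates, and the opening of the AE sentence marks an exception to the general rule. The one real clash is giving 1 July to a date with no year, and it goes once the triggers are corrected.
- *Half of all such durations would be negative.* That holds only for events that start and stop on the same day. The share falls quickly with duration and is zero at 21 days.
- *Mean duration would be biased materially downward.* The net shift is about -0.7 day for a missing stop day, and +0.7 for a missing onset day.
- *A missing day is the commonest case, and duration is a headline safety result.* The documents give no partial-date rate. The legible text of SAP 9.2.1 names incidence, type, relationship and severity, not duration.

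Parts of SAP 9.2.1 and the appendices are redacted, so a bound there cannot be excluded. Protocol 13.2.2 and 14.2 also have monitors review worksheets and eCRFs and query omissions, which should reduce the number of partial dates. Both points limit the impact without repairing the rule.

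**Conclusion.** The point holds as a minor defect. The AE-duration rule cannot be computed as written. On its evident intention it can give impossible values: about 41%, 28%, 5% and 0% of 3-, 7-, 14- and 21-day events with a missing stop day.

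These shares assume uniform onset days and fixed true durations. They apply only to events with that kind of partial date, whose number is unknown. Only descriptive AE durations are touched. AE incidence and the primary endpoint are not affected. The secure harm is impossible individual values and unplanned handling of them, not a large bias in the mean.

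**What to change.** Replace the AE sentence in SAP 9.3.10 with the following rule, and state that it is the AE-specific exception to the general partial-date sentence.

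1. Day missing: use the 15th of the known month.
2. Day and month missing: use 1 July of the known year.
3. Year missing: do not impute, and report duration as missing.
4. An imputed onset may be no earlier than informed consent and no later than a known stop.
5. An imputed stop may be no earlier than onset and no later than the last follow-up contact for that event. If both dates are partial, impute onset first.

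The bounds are chosen to fit the rest of the plan. First injection would be the wrong lower limit, because AEs are recorded from consent (Protocol 9.6.7.1, SAP 9.2.1) and controls are untreated until after the Week 8 evaluation (SAP 2.1). The last scheduled visit would be the wrong upper limit, because device-related AEs may be followed beyond it (Protocol 9.6.6.1).

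The cost is one SAP paragraph and a few lines of code. There is a small downside: flooring at onset raises the mean of very short events when only the day is missing (3 days becomes 5.0). The rise is large when the month is missing too. The tables should therefore report the number of AEs with imputed dates, split into day only and day plus month, and repeat the duration summary without the second group.
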